8.1.6 Assignment of Screening Number

All consented participants will be given a unique screening number that will be used to identify the participant for all procedures that occur prior to randomization. Each participant will be assigned only 1 screening number. Screening numbers must not be re-used for different participants.

8.1.7 Assignment of Treatment/Randomization Number

All eligible participants will be randomly allocated and will receive a treatment/randomization number. The treatment/randomization number identifies the participant for all procedures occurring after treatment randomization. Once a treatment/randomization number is assigned to a participant, it can never be re-assigned to another participant.

A single participant cannot be assigned more than 1 treatment/randomization number.

8.1.8 Study Intervention Administration

For infusion:

Pembrolizumab 200 mg will be administered in 30 minutes, with a window of -5 minutes and +10 minutes, as an IV infusion on Day 1 of each 21-day cycle. Do not administer pembrolizumab as an IV push nor as a bolus injection. Administration of study medication

will be monitored by the investigator and/or study staff. The total volume of study intervention infused will be compared to the total volume prepared to determine compliance with each dose administered. Please refer to the pembrolizumab (MK-3475) Pharmacy Manual.

For IT injection:

Refer to Section 6 for MK-1454 dose and treatment details, and to the SoA (Section 1.3) for timing of IT injections. Guidelines for prioritization of lesions for IT injection are provided in Appendix 8.

8.1.8.1 Timing of Dose Administration

See the SoA in Section 1.3.

8.1.9 Discontinuation and Withdrawal

Participants who discontinue study intervention prior to completion of the treatment period should be encouraged to continue to be followed for all remaining study visits as outlined in the SoA and Section 8.10.3.

When a participant withdraws from participation in the study, all applicable activities scheduled for the End of Treatment/Discontinuation visit should be performed (at the time of withdrawal). Any AEs that are present at the time of withdrawal should be followed in accordance with the safety requirements outlined in Section 8.4.3.

8.1.9.1 Withdrawal From Future Biomedical Research

Participants may withdraw their consent for future biomedical research. Participants may withdraw consent at any time by contacting the investigator for the main study. If medical records for the main study are still available, the investigator will contact the Sponsor using the designated mailbox ([contact]). Subsequently, the participant's consent for FBR will be withdrawn. A letter will be sent from the Sponsor to the investigator confirming the withdrawal. It is the responsibility of the investigator to inform the participant of completion of withdrawal. Any analyses in progress at the time of request for withdrawal or already performed prior to the request being received by the Sponsor will continue to be used as part of the overall research study data and results. No new analyses would be generated after the request is received.

In the event that the medical records for the main study are no longer available (eg, if the investigator is no longer required by regulatory authorities to retain the main study records) or the specimens have been completely anonymized, there will no longer be a link between the participant's personal information and their specimens. In this situation, the request for specimen withdrawal cannot be processed.

8.1.10 Participant Blinding/Unblinding

This is an open-label study; there is no blinding for this study.

8.1.11 Calibration of Equipment

The investigator or qualified designee has the responsibility to ensure that any device or instrument used for a clinical evaluation/test during a clinical study that provides information about inclusion/exclusion criteria and/or safety or efficacy parameters shall be suitably calibrated and/or maintained to ensure that the data obtained are reliable and/or reproducible. Documentation of equipment calibration must be retained as source documentation at the study site.

8.2 Efficacy/Immunogenicity Assessments

8.2.1 Tumor Imaging and Assessment of Disease

Tumor imaging should be acquired by CT (strongly preferred). MRI should be used when CT is contraindicated or for imaging of the brain. The same imaging technique, ie, modality and use of contrast, should be used for a participant throughout the study to optimize the visualization of existing and new tumor burden. Required anatomical images, as well as the process for image collection and transmission to the iCRO, can be found in the Site Imaging Manual.

8.2.2 Initial Tumor Imaging

The process for image collection and transmission to the central vendor can be found in the Site Imaging Manual. Tumor imaging may be performed by CT (preferred) or MRI; however, the same imaging technique should be used on a participant throughout the study. CT scan is the more commonly used modality and is preferred for the majority of subjects. An MRI can be utilized, if clinically appropriate.

Imaging should include the head and neck, chest, and abdomen at all timepoints specified in the Study Flow Chart. Imaging of the pelvis is optional. For an individual participant, imaging should be consistent at all timepoints, (ie, follow-up imaging should cover the same areas as the baseline area, using the same imaging modality).

Initial tumor imaging at screening must be performed within 28 days prior to the date of allocation. The screening imaging must be submitted to the iCRO for confirmation of measurable disease per RECIST 1.1 for eligibility prior to randomization. Tumor imaging performed as part of routine clinical management is acceptable for use as screening tumor imaging if they are of diagnostic quality and performed within 28 days prior to the date of randomization.

Participants with previously treated brain metastases may participate provided they have stable brain metastases (ie, without evidence of progression by imaging confirmed by MRI if MRI was used at prior imaging, or confirmed by CT imaging if CT was used for prior imaging) for at least 4 weeks prior to the first dose of study intervention. Any neurologic symptoms must have returned to baseline, and participants must have no evidence of new or enlarging brain metastases and have not used steroids for brain metastases for at least 14 days prior to study initiation, as per local site assessment. This exception does not include

carcinomatous meningitis, as participants with carcinomatous meningitis are excluded regardless of clinical stability.

8.2.3 Tumor Imaging During the Study

The first on-study imaging assessment should be performed at 6 weeks (42-49 days) from the date of first dose. Subsequent tumor imaging should be performed every 6 weeks (42 days \pm 7 days) (or more frequently if clinically indicated). After 1 year, participants who remain on treatment will have imaging performed every 9 weeks (63 days \pm 7 days). Imaging timing should follow **calendar days** and should not be adjusted for delays in cycle starts. Imaging should continue to be performed until disease progression is identified by the investigator, the start of new anticancer treatment, withdrawal of consent, or death, or notification by the Sponsor, whichever occurs first. All supplemental imaging must be submitted to the iCRO.

Objective response should be confirmed by a repeat imaging assessment. Tumor imaging to confirm PR or CR should be performed at least 4 weeks after the first indication of response is observed. Participants will then return to regularly scheduled imaging, starting with the next scheduled imaging time point. Participants who receive additional imaging for confirmation do not need to undergo the next scheduled tumor imaging if it is less than 4 weeks later; tumor imaging may resume at the subsequent scheduled imaging time point. Note: Response does not typically need to be verified in real time by the BICR.

Per iRECIST (Section 8.2.5), disease progression should be confirmed by the site 4 to 8 weeks after site-assessed first radiologic evidence of PD in clinically stable participants. Participants who have unconfirmed disease progression may continue on treatment at the discretion of the investigator until progression is confirmed, provided they have met the conditions detailed in Section 8.2.5. Participants who receive confirmatory imaging do not need to undergo the next scheduled tumor imaging if it is less than 4 weeks later; tumor imaging may resume at the subsequent scheduled imaging time point, if clinically stable. Participants who have confirmed disease progression by iRECIST, as assessed by the site, will discontinue the treatment. Exceptions are detailed in Section 8.2.5.

8.2.4 End of Treatment and Follow-up Tumor Imaging

In participants who discontinue study intervention, tumor imaging should be performed at the time of intervention discontinuation (\pm 4-week window). If previous imaging was obtained within 4 weeks prior to the date of discontinuation, then imaging at intervention discontinuation is not mandatory. For participants who discontinue study intervention due to documented disease progression, this is the final required tumor imaging if the investigator elects to not implement iRECIST.

For participants who discontinue study intervention without documented disease progression, every effort should be made to continue monitoring their disease status by tumor imaging using the same imaging schedule used while on treatment (every 6 weeks in Year 1 or 9 weeks after Year 1). Monitor disease status until the start of a new anticancer treatment, disease progression, pregnancy, death, withdrawal of consent, or the end of the study, whichever occurs first.

8.2.5 iRECIST 1.1 Assessment of Disease

iRECIST is based on RECIST 1.1, but adapted to account for the unique tumor response seen with immunotherapeutic drugs. iRECIST will be used by investigator/local radiology reviewers to assess tumor response and progression, and to make treatment decisions. When clinically stable, participants should not be discontinued until progression is confirmed by the investigator, working with local radiology, according to the rules outlined below. This allowance to continue treatment despite initial radiologic PD takes into account the observation that some participants can have a transient tumor flare in the first few months after the start of immunotherapy, and then experience subsequent disease response. These data will be collected and captured in the clinical database.

For participants who show evidence of radiological PD by RECIST 1.1 as determined by the investigator, the investigator will decide whether to continue a participant on study intervention until repeat imaging is obtained using iRECIST for participant management (see [Table 9](#) and [Figure 3](#)). This decision by the investigator should be based on the participant's overall condition.

Clinical stability is defined as the following:

- Absence of symptoms and signs indicating clinically significant progression of disease
- No decline in ECOG performance status
- No requirements for intensified management, including increased analgesia, radiation, or other palliative care

Any participant deemed clinically unstable should be discontinued from study intervention at site-assessed first radiologic evidence of PD and is not required to have repeat imaging for confirmation of PD by iRECIST.

If the investigator decides to continue treatment, the participant may continue to receive study intervention and the tumor assessment should be repeated 4 to 8 weeks later to confirm PD by iRECIST per investigator assessment. Images should continue to be sent in to the central imaging vendor for potential retrospective BICR.

Tumor flare may manifest as any factor causing radiographic progression per RECIST 1.1, including:

- Increase in the sum of diameters of target lesion(s) identified at baseline to $\geq 20\%$ and ≥ 5 mm from nadir
 - Note: the iRECIST publication uses the terminology “sum of measurements”, but “sum of diameters” will be used in this protocol, consistent with the original RECIST 1.1 terminology.
- Unequivocal progression of nontarget lesion(s) identified at baseline

- Development of new lesion(s)

iRECIST defines new response categories, including iUPD (unconfirmed progressive disease) and iCPD (confirmed progressive disease). For purposes of iRECIST assessment, the first visit showing progression according to RECIST 1.1 will be assigned a visit (overall) response of iUPD, regardless of which factors caused the progression.

At this visit, target and nontarget lesions identified at baseline by RECIST 1.1 will be assessed as usual.

New lesions will be classified as measurable or nonmeasurable, using the same size thresholds and rules as for baseline lesion assessment in RECIST 1.1. From measurable new lesions, up to 5 lesions total (up to 2 per organ), may be selected as New Lesions Target. The sum of diameters of these lesions will be calculated, and kept distinct from the sum of diameters for target lesions at baseline. All other new lesions will be followed qualitatively as New Lesions Nontarget.

Assessment at the Confirmatory Imaging

On the confirmatory imaging, the participant will be classified as progression confirmed (with an overall response of iCPD), or as showing persistent unconfirmed progression (with an overall response of iUPD), or as showing disease stability or response (iSD/iPR/iCR).

Confirmation of Progression

Progression is considered confirmed, and the overall response will be iCPD, if ANY of the following occurs:

- Any of the factors that were the basis for the initial iUPD show worsening:
 - For target lesions, worsening is a further increase in the sum of diameters of ≥ 5 mm, compared to any prior iUPD time point
 - For nontarget lesions, worsening is any significant growth in lesions overall, compared to a prior iUPD time point; this does not have to meet the “unequivocal” standard of RECIST 1.1
 - For new lesions, worsening is any of these:
 - An increase in the new lesion sum of diameters by ≥ 5 mm from a prior iUPD time point
 - Visible growth of new nontarget lesions
 - The appearance of additional new lesions
- Any new factor appears that would have triggered PD by RECIST 1.1

Persistent iUPD

Progression is considered not confirmed, and the overall response remains iUPD, if:

- None of the progression-confirming factors identified above occurs AND
- The target lesion sum of diameters (initial target lesions) remains above the initial PD threshold (by RECIST 1.1)

Additional imaging for confirmation should be scheduled 4 to 8 weeks from the imaging on which iUPD is seen. This may correspond to the next visit in the original visit schedule. The assessment of the subsequent confirmation scan proceeds in an identical manner, with possible outcomes of iCPD, iUPD, and iSD/iPR/iCR.

Resolution of iUPD

Progression is considered not confirmed, and the overall response becomes iSD/iPR/iCR if:

- None of the progression-confirming factors identified above occurs, AND
- The target lesion sum of diameters (initial target lesions) is not above the initial PD threshold

The response is classified as iSD or iPR (depending on the sum of diameters of the target lesions), or iCR if all lesions resolve.

In this case, the initial iUPD is considered to be pseudoprogression, and the level of suspicion for progression is “reset”. This means that the next visit that shows radiographic progression, whenever it occurs, is again classified as iUPD by iRECIST, and the confirmation process is repeated before a response of iCPD can be assigned.

Management Following the Confirmatory Imaging

If repeat imaging does not confirm PD per iRECIST, as assessed by the investigator, and the participant continues to be clinically stable, study intervention may continue and follow the regular imaging schedule. If PD is confirmed, participants will be discontinued from study intervention.

Note: If a participant has confirmed radiographic progression (iCPD) as defined above, but the participant is achieving a clinically meaningful benefit, an exception to continue treatment may be considered following consultation with the Sponsor. In this case, if study intervention is continued, tumor imaging should continue to be performed following the intervals as outlined in Section 1.3 and submitted to the central imaging vendor.

Detection of Progression at Visits after Pseudoprogession Resolves

After resolution of pseudoprogession (ie, achievement of iSD/iPR/iCR), iUPD is indicated by any of the following events:

- Target lesions
 - Sum of diameters reaches the PD threshold (20% and 5 mm increase from nadir) either for the first time, or after resolution of previous pseudoprogession. The nadir is always the smallest SOD seen during the entire study, either before or after an instance of pseudoprogession.
- Nontarget lesions
 - If nontarget lesions have never shown unequivocal progession, their doing so for the first time results in iUPD
 - If nontarget lesions had shown previous unequivocal progession, and this progession has not resolved, iUPD results from any significant further growth of nontarget lesions, taken as a whole
- New lesions
 - New lesions appear for the first time
 - Additional new lesions appear
 - Previously identified new target lesions show an increase of ≥ 5 mm in the new lesion sum of diameters, from the nadir value of that sum
 - Previously identified nontarget lesions show any significant growth

If any of the events above occur, the overall response for that visit is iUPD, and the iUPD evaluation process (see Assessment at the Confirmatory Imaging above) is repeated. Progession must be confirmed before iCPD can occur.

[figure not shown]
The decision process is identical to the iUPD confirmation process for the initial PD, with one exception: if new lesions occurred at a prior instance of iUPD, and at the confirmatory imaging the burden of new lesions has increased from its smallest value (for new target lesions, the sum of diameters is ≥ 5 mm increased from its nadir), then iUPD cannot resolve to iSD or iPR. It will remain iUPD until either a decrease in the new lesion burden allows resolution to iSD or iPR, or until a confirmatory factor causes iCPD. If any of the factors above indicate iUPD, the iUPD evaluation process repeats, just as on the first occurrence of iUPD.

Additional details about iRECIST are provided in the iRECIST publication.

Table 9 Imaging and Treatment after First Radiologic Evidence of Progressive Disease

	Clinically Stable		Clinically Unstable	
	Imaging	Treatment	Imaging	Treatment
First radiologic evidence of PD by RECIST 1.1	Repeat imaging at 4 to 8 weeks to confirm PD per iRECIST	May continue study intervention at the local site investigator's discretion and after obtaining participant's consent	Repeat imaging at 4 to 8 weeks to confirm PD per physician discretion only	Discontinue treatment
Repeat tumor imaging confirms PD (iCPD) by iRECIST per local assessment	No additional imaging required	Discontinue treatment (exception is possible upon consultation with Sponsor)	No additional imaging required	Not applicable
Repeat tumor imaging shows iUPD by iRECIST, per local assessment	Repeat imaging at 4 to 8 weeks to confirm PD	Continue study intervention at the local site investigator's discretion	No additional imaging required	Discontinue treatment
Repeat tumor imaging shows iSD, iPR, or iCR by iRECIST per local assessment	Continue regularly scheduled imaging assessments	Continue study intervention at the local site investigator's discretion	No additional imaging required	Discontinue treatment
iCPD immune confirmed progressive disease; iCR immune complete response; iSD immune stable disease; iRECIST immune related response evaluation criteria in solid tumors; iUPD immune unconfirmed progressive disease; PD progressive disease; PFS progression free survival; iPR immune partial response.				

Figure 3 Imaging and Treatment for Clinically Stable Participants after First Radiologic Evidence of PD Assessed by the Investigator

iCRO = imaging contract research organization; iCR = immune complete response; iPR = immune partial response; iSD = immune stable disease; iUPD = immune unconfirmed progressive disease; PD = progressive disease; iRECIST = Response Evaluation Criteria in Solid Tumors 1.1 for immune-based therapeutics; RECIST = Response Evaluation Criteria in Solid Tumors

8.2.6 itRECIST

itRECIST is a response assessment that is tailored to intratumoral immunotherapy, is aligned with RECIST 1.1 overall response assessment [Goldmacher, G. V., et al 2020], and is further described in Section 10.10.

itRECIST

- provides a guidance on baseline categorization of target and nontarget lesions (Figure 5)
- provides guidance on recategorization of lesions during therapy (Figure 6)
- allows for separate response assessment in injected and noninjected lesions (Figure 7)
- for injected lesions, provides an iterative response assessment process that adapts to changes in lesion selection for intratumoral immunotherapy (an example is provided in Figure 8)
- provides guidelines on prioritization of lesion injection during the course of intratumoral immunotherapy (see Section 10.8)

itRECIST supports standardized collection of data from intratumoral immunotherapy clinical studies to facilitate exploratory response analysis.

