9.6.1.5 Analysis Strategy for Key Efficacy Endpoints

Table 13 summarizes the analysis strategy for the primary and secondary efficacy endpoints.

Table 13 Analysis Strategy for Key Efficacy Variables

Endpoint/Variable	Statistical Method	Analysis Population	Missing Data Approach
Primary Analyses			
OR/ORR (RECIST 1.1 by BICR)	Test and estimation: Stratified Miettinen and Nurminen method.	ITT	Participants with missing data are considered nonresponders.
Secondary Analyses			
PFS (RECIST 1.1 by BICR)	Summary statistics using Kaplan-Meier method Estimation: stratified Cox model with Efron's tie-handling method	ITT	Censored according to rules in Table 11 .
DOR (RECIST 1.1 by BICR)	Summary statistics using Kaplan-Meier method	All responders in ITT	Censored according to rules in Table 12 .
OS	Summary statistics using Kaplan-Meier method Estimation: stratified Cox model with Efron's tie-handling method	ITT	Censored at last known alive date.
BICR blinded independent central review; DOR duration of response; ITT intention to treat; ORR objective response rate; OS overall survival; PFS progression free survival; RECIST 1.1 Response Evaluation Criteria in Solid Tumors Version 1; iRECIST modified RECIST 1.1 for immune based therapeutics. Sensitivity analyses will be performed for ORR, PFS, and DOR using RECIST 1.1 and iRECIST based on investigator's assessment.			

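### Under the iRECIST rules in Section 8.2.5, a new or nontarget lesion that triggered the first progression and persists without worsening is relabelled pseudoprogression whenever the target sum is below the PD threshold

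*Combined protocol and SAP*

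**What the plan says.** Section 8.2.5 sets out the steps for iRECIST.

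- **First progression.** The first visit with RECIST 1.1 progression is "assigned a visit (overall) response of iUPD, regardless of which factors caused the progression". The listed factors are target-lesion growth, unequivocal nontarget progression and new lesions.
- **Confirmation (iCPD).** This needs worsening of a factor behind the iUPD, or a new factor that would itself be PD. Worsening means at least 5 mm more in the target sum, significant nontarget growth, at least 5 mm more in the new-lesion sum, visible growth of new nontarget lesions, or additional new lesions.
- **Persistent iUPD.** No confirming factor occurs, and the initial target sum is still above the PD threshold.
- **Resolution.** No confirming factor occurs, and "The target lesion sum of diameters (initial target lesions) is not above the initial PD threshold". The visit becomes iSD or iPR according to the target sum. Only iCR requires every lesion to have gone. On resolution "the initial iUPD is considered to be pseudoprogression", and the next progression starts again as iUPD.

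The stated reason for tolerating a first PD is that "some participants can have a transient tumor flare in the first few months after the start of immunotherapy", followed by response.

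Section 4.1 says that ORR, PFS and DOR will also be assessed by iRECIST. The footnote to Table 13 (Section 9.6.1.5) adds: "Sensitivity analyses will be performed for ORR, PFS, and DOR using RECIST 1.1 and iRECIST", based on the investigator's assessment.

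**The concern.** Three kinds of event can open an iUPD, but once nothing has worsened only one quantity, the initial target sum, decides whether it stays open. If the trigger was a new or nontarget lesion, the target sum may never have been above the threshold. Persistent iUPD is then out of reach, and an unchanged lesion closes the iUPD although the finding that caused it is still there.

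The same persistence therefore gets opposite labels depending on which lesion progressed. A lesion that stays is also hard to describe as a transient flare.

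What is at stake is the content of the iRECIST sensitivity analyses. A participant with a persisting new metastasis can enter as iSD or iPR. If the derivation follows the printed rules, the earlier iUPD may also drop out as a progression event.

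**Working it through.** The plan gives no figure to reproduce, so the check applies the printed rules in order (iCPD, then persistent iUPD, then resolution) to test cases at the first confirmatory scan.

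**Inputs.**
- PD threshold, from 8.2.5: an increase of at least 20% and at least 5 mm from nadir, so threshold = max(1.2 × nadir, nadir + 5).
  - Nadir 50 mm: max(60, 55) = 60 mm.
  - Nadir 40 mm: max(48, 45) = 48 mm.
- Confirming factors: as listed in 8.2.5.
- Illustrative assumptions, not trial data: baseline target sum 60 mm, and new-lesion sum 20 mm at iUPD. The partial-response cut is taken as a 30% fall from baseline, 0.7 × 60 = 42 mm.

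| Trigger of iUPD | Target sum: nadir / iUPD / confirmatory (mm) | Threshold (mm) | Trigger at confirmatory scan | Result |
|---|---|---|---|---|
| Target growth | 50 / 62 / 62 | 60 | unchanged | iUPD persists |
| Target growth | 50 / 62 / 55 | 60 | back below threshold | iSD |
| New lesion | 50 / 55 / 55 | 60 | 20 to 20 mm | iSD |
| New lesion | 40 / 40 / 40 | 48 | 20 to 20 mm | iPR (40 ≤ 42) |
| New measurable lesion | 50 / 55 / 55 | 60 | 20 to 24 mm (+4) | iSD |
| New measurable lesion | 50 / 55 / 55 | 60 | 20 to 25 mm (+5) | iCPD |
| New lesion | 50 / 55 / 55 | 60 | additional new lesion | iCPD |
| Nontarget progression | 50 / 55 / 55 | 60 | unchanged | iSD |
| Nontarget progression | 40 / 40 / 40 | 48 | unchanged | iPR (40 ≤ 42) |
| Nontarget progression | 50 / 55 / 55 | 60 | further significant growth | iCPD |

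In the first row the target sum was 12 mm (24%) above nadir at iUPD and did not change, so iUPD stays. In the new-lesion and nontarget rows marked unchanged, the trigger persisted just as fully, yet the visit is iSD or iPR. In these cases an unchanged cause keeps iUPD open only when that cause is the target sum.

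**Does other text close the gap?** The later part of 8.2.5, on progression after pseudoprogression has resolved, contains an exception under which new-lesion burden blocks resolution to iSD or iPR. It applies at a later iUPD, when new lesions occurred at a prior one, and it needs the burden to have increased (at least 5 mm from nadir for new target lesions). It covers neither the first confirmatory scan nor an unchanged lesion. The same part gives a rule for nontarget progression that is still unresolved at that stage, so it presupposes the state that the resolution rule calls resolved.

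**The case against.** The strongest objections, and what stands of each:

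- **Resolution does not look only at target lesions.** Correct. The first condition also requires that nontarget and new lesions have not worsened. For a lesion that persists without worsening, that condition is met automatically, and the target sum is the only test left. The allowance for growth below 5 mm applies to measurable new lesions; visible growth of new nontarget lesions confirms progression.
- **The wording may be deliberate.** It may. The section anticipates persisting lesions and refers to the iRECIST publication for further detail. Whether the rule departs from that publication cannot be judged from these documents and is not claimed here. A deliberate rule would still need squaring with the flare rationale and with the term pseudoprogression.
- **The later exception limits repeated resolution.** It does, but only from a second iUPD onward.
- **The consequences are small.** This largely stands. Regular first-year imaging is every 6 weeks (Section 8.2.3), inside the 4 to 8 week confirmation window, so scan dates move little.

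A reader might infer a bias towards Arm 1, because only Arm 1 lesions are injected. The documents do not establish this. Shrinking targets beside a stable new lesion can also occur on pembrolizumab alone. In Arm 1, new or progressing lesions are prioritised for injection (Section 6.2.1, Appendix 8), and noninjected target lesions also shrank in the first-in-human study (Section 2.2.3.1). An imbalance is possible in principle, but neither its presence nor its direction is shown.

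**Conclusion.** The point holds as a classification inconsistency in 8.2.5. It needs three things together: a first iUPD triggered by a new or nontarget lesion, a target sum below the PD threshold at the confirmatory scan, and a trigger that persists without worsening. The visit then becomes iSD or iPR where an equally persistent target progression stays iUPD. A later worsening also opens a fresh iUPD that needs its own confirmation, one scan more than if the iUPD had stayed open.

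The reach is narrow. The primary ORR and the secondary PFS and DOR use RECIST 1.1 by blinded central review (Section 9.4.1), so they are unaffected, as are power and type I error. What is affected is the investigator-based iRECIST sensitivity analyses and site imaging and management.

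A reader might want to put a percentage on the participants reclassified. That would need the share of first progressions driven by new or nontarget lesions, the share rescanned and the share unchanged; the documents give none of these. Nor would every such participant add to the iRECIST ORR: those classified iSD would not, and a response needs confirmation at least 4 weeks later (Section 8.2.3). Loss of a PFS event assumes that a resolved iUPD is not counted, which the text of Section 9 available for review does not specify.

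**What to change.** **Analysis.** In the derivation of the iRECIST ORR, PFS and DOR, do not count a visit as iSD or iPR, and do not cancel the earlier iUPD, while the new or nontarget lesion that triggered it persists. Keep the visit as iUPD. State the rule where the iRECIST sensitivity analyses are specified, and state there how an iUPD that is neither confirmed nor resolved counts in PFS and DOR.

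**Cost.** A small amount of programming on lesion data that 8.2.5 already says will be captured, and iRECIST figures that may be slightly less favourable.

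**Site management.** Separately, ask the sponsor to reconcile the passages of 8.2.5 on the flare rationale, first progression, persistent iUPD, resolution, and progression after pseudoprogression. This review proposes no rule for continuing or stopping treatment. For clinically stable participants Table 9 gives the same treatment entry for iUPD and for iSD, iPR or iCR, but the label still affects when iCPD, and with it discontinuation, is reached. That choice belongs to the sponsor.
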